6.3 Subject exclusion criteria

Investigators, sponsors, data management and statistical analysis units comprehensively judge whether to exclude patients based on factors such as the degree to which subjects completed the trial and the reasons for withdrawal. FAS subjects shall be excluded from PPS if they meet one of the following:

- (1) Subjects who do not meet the inclusion criteria or meet any of the exclusion criteria are mistakenly included in the trial;
- (2) Subjects with missing primary efficacy indicators;
- (3) Subjects who are in major violation of the trial protocol and with poor compliance;
- (4) Subjects with other special reasons.

Specific subject exclusion will be determined through discussion between the investigator, sponsor, data administrator and statistician at the data review meeting.

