18.1 Basic document management
18.2 Finance and insurance
Investigator's Statement

Abbreviations	Definition	
AE	Adverse Event	
CRC	Clinical Research Coordinator	
CRO	Contract Research Organization	
D	Day	
DMP	Data Management Plan	
eCRF	Electronic Case Report Form	
EDC	Electronic Data Collection	
FAS	Full Analysis Set	
GCP	Good Clinical Practice (Medical Device)	
ICF	Informed Consent Form	
MedDRA	Medical Dictionary for Regulatory Activities	
mL	Milliliter	
NMPA	National Medical Products Administration	
PASS	Power Analysis and Sample Size (Statistics Software)	
PPS	Per Protocol Set	
PT	Preferred term	
SAE	Serious Adverse Event	
SAS	Statistical Analysis System (Statistics Software)	
SOC	System Organ Class	
SS	Safety Set	
°C	Celsius	

List of Abbreviations

Synopsis

Study Title	A Prospective, Multi-center, Randomized, Open-label, Parallel-controlled Clinical Study of Pre-filled Flush Syringes
Protocol No.	MDS-21FLUSHCN01
Sponsor	BD Medical Technology (Jiangsu) Co., Ltd.
Study Sites	3 study sites
Planned Study Period	April 2022 to September 2023
Subject Population	Subjects requiring locking and flushing the end of catheter line at the intervals of different drug treatment.
Study Objective	To compare the BD PosiFlush [™] Pre-filled Flush Syringes (manufactured by BD, USA) with the pre-filled flush syringes (manufactured by BD Medical Technology (Jiangsu) Co., Ltd.) and evaluate the effectiveness and safety for locking and flushing the end of catheter line.
Study Design	This prospective, multi-center, randomized, open, and parallel- controlled clinical study is intended to evaluate the effectiveness and safety of pre-filled flush syringes. After signing of informed consent form, all subjects who meet the inclusion criteria and do not meet the exclusion criteria are randomized
	into the investigational group or control group in a 1:1 ratio. This study is performed by 63 trial nurses using the study device (investigational device and control device) to lock and flush the end of catheter line for all subjects, each nurse will randomly use 3 investigational devices and 3 control devices.
Number of subjects planned to be enrolled	 Sample size calculation assumptions: Overall performance success rate in the investigational device group is 98% Overall performance success rate in the control device group is 98% Non-inferiority margin is 5%
	 Allocation ratio of 1:1
	• Type I error rate is 0.025 one-side
	• Power is 90%
	• Attrition rate is 10%

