8.8 Blind review

Not applicable.

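### Protocol 6.3 allows removal from the primary analysis set on an undefined ground, with no stated masking or timing of the review, and the SAP's definition of that set does not match

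*Protocol*

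**What the plan says.** **Grounds.** Protocol 6.3 removes a subject from the PPS for an eligibility error, a missing primary outcome, or a major protocol violation with poor compliance. It then adds a fourth ground: "Subjects with other special reasons". No definition, example or limit follows.

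**Who decides.** The same section states: "Specific subject exclusion will be determined through discussion between the investigator, sponsor, data administrator and statistician at the data review meeting".

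**Why the set matters.** Protocol 6.2 and SAP 5.2 both make the PPS primary for the primary endpoint. The FAS is also analysed (Protocol 6.2, SAP 6.3.1), but neither document requires success in both sets.

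**Blinding.** Protocol 5.1 describes an open design. Under Protocol 5.3.1 and 5.5.2, the study nurse who uses the syringe also answers the five performance questions. Protocol 8.8, on blind review, reads in full "Not applicable". Protocol 8.9 describes database lock without placing the data review meeting before or after it.

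**What the SAP says.** SAP 5.2 defines the PPS by three conditions: no serious protocol violation, good compliance, and a complete primary outcome. The protocol's own definition in 6.2 has the same three. Neither includes the fourth ground. SAP Table 6.1, Scenario 3, classes a subject with any unfavourable answer as *Fail* and includes that subject in the PPS. SAP 9 presents the SAP as more detail on the protocol and does not say that it overrides Protocol 6.3.

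**The concern.** Membership of the primary set should be fixed by rules that cannot respond to the result. Here one ground is unlimited, the deciding parties include the sponsor and investigators of an open trial, and no step keeps arm or outcome out of view. A failed test subject removed from the PPS improves the primary estimate directly. With an expected failure rate of 2%, each arm should have only a handful of failures, so one or two discretionary removals can carry the lower confidence limit across -5%.

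The two documents also give different rules for the same set. A subject with an assessed failure stays in under Table 6.1 but could be taken out under Protocol 6.3.

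**Working it through.** **1. Inputs.** From the Protocol Synopsis and 6.1: "Type I error rate is 0.025 one-side", power 90%, success rate 98% in both arms, margin 5 percentage points, 1:1 allocation, 10% drop-out. From SAP 3.3: 189 per arm. From SAP 6.3.1: a Wald two-sided 95% interval when sites are pooled, with non-inferiority if the lower limit exceeds -5%.

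**2. The plan's own figure.** With unpooled variance,

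n = (1.960 + 1.282)² × (0.98×0.02 + 0.98×0.02) / 0.05² = 10.507 × 0.0392 / 0.0025 = 164.8, so 165 per arm.

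165 / 0.9 = 183.3, so 184 per arm and 368 in total. 63 nurses × 6 devices = 378, or 189 per arm. The plan's sample size is reproduced.

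**3. Expected failures.** 0.02 × 165 = 3.3 and 0.02 × 189 = 3.8 per arm.

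**4. Effect of removing failed test subjects.** The lower limit is L = (p1 − p2) − 1.960 × √[p1(1−p1)/n1 + p2(1−p2)/n2].

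Worked case, 8 test and 5 control failures of 189:
- Before: p1 = 181/189, p2 = 184/189, difference -1.587%, standard error 1.873%, L = -1.587 − 1.960×1.873 = -5.26%. Not met.
- One failed test subject removed: p1 = 181/188, difference -1.078%, standard error 1.808%, L = -4.62%. Met.

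| Per arm | Test v control failures | L before | Test failures removed | L after |
|---|---|---|---|---|
| 189 | 8 v 5 | -5.26% | 1 | -4.62% |
| 189 | 7 v 3 | -5.35% | 1 | -4.68% |
| 189 | 8 v 4 | -5.64% | 2 | -4.35% |
| 170 (assumed) | 6 v 3 | -5.17% | 1 | -4.43% |

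The 170 is an assumed PPS size (189 × 0.9 = 170.1); the documents do not give it.

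**5. How often one removal would decide the result.** By exact binomial enumeration, this is the chance that the criterion is missed but would be met after dropping one failed test subject (control rate 98%):

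| True test failure rate | 170 per arm | 189 per arm |
|---|---|---|
| 2% (as planned) | about 6% | about 4% |
| 3% to 4% | about 13% to 15% | about 9% to 11% |

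**6. Worst-case effect on a false claim.** True rates are set on the margin (93% v 98%), and the stated number of failures is removed from the test arm only, in every trial. The number removed is an assumption, shown as a range.

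| Failures removed | 189 per arm | 165 per arm |
|---|---|---|
| 0 | 3.9% | 4.1% |
| 1 | 6.5% | 8.0% |
| 2 | 11.0% | 14.0% |
| 3 | 17.4% | 18.9% |

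The first row exceeds the nominal 2.5% because of the Wald interval, which is a separate matter. Only the rise down each column belongs to this point.

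**The case against.** The case against has several parts.

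- *No sentence says that arm and outcome are shown at the meeting.* This is correct. A reader might infer from Protocol 8.8 that the meeting works from unmasked outcomes, but that entry may only record that an open trial has no treatment blind to review. What the documents support is that masking and timing are not stated, so exclusion with knowledge of both is possible.
- *No sentence permits exclusion because of the outcome.* Also correct. Protocol 6.3 opens by pointing to how far the subject completed the trial and why the subject withdrew, neither of which is device performance. But those factors are given as examples, and the fourth ground has no limit.
- *The SAP already closes the gap.* In part. SAP 5.2 has no fourth ground, and Table 6.1 keeps an assessed failure in the PPS. But Table 6.1 deals with the answers to the five questions, and the SAP does not withdraw Protocol 6.3. The documents conflict, and neither is stated to prevail.
- *The FAS is analysed, and SAP 6.2.1 lists everyone left out of the PPS.* These are real safeguards. They make a removal visible but do not prevent it, because the PPS is primary and agreement with the FAS is not required.
- *The numerical examples are knife-edge cases.* They are. At the planned rates, one removal would be decisive in about 4% to 6% of trials.

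**Conclusion.** The point holds as a defect in the rule. Protocol 6.3 lets parties to an open-label trial remove subjects from the primary set on an undefined ground, at a review with no stated masking or timing, and this does not match SAP 5.2 and Table 6.1. One such removal can reverse the conclusion (-5.26% to -4.62% at 189 per arm; -5.17% to -4.43% at an assumed 170), though near-margin results of that kind are occasional rather than typical.

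The figures rest on the SAP's pooled Wald interval, independent subjects, and removal of failures from the test arm only. A reader might go further and conclude that the meeting will see arm and outcome, or that the plan provides for outcome-based exclusion. The documents say neither, and nothing in them suggests intent. The change should be made, because the present wording leaves the primary result open to a doubt that a few lines of text would remove.

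**What to change.** 1. Delete ground (4) from Protocol 6.3, so that it agrees with SAP 5.2 and Table 6.1. The SAP has no such ground to delete.
2. State in both documents that a subject with an assessed *Fail* is not excluded because of that result.
3. Settle all exclusions before database lock, on a listing that hides treatment arm and the five performance answers. Show a missing primary outcome only as a yes/no flag. Apply this also to ground (3): what counts as a major violation remains a judgement, and the note in SAP 5.2 ties it to effect on the primary evaluation, so deleting ground (4) alone would leave discretion in place.
4. Amend Protocol 8.8 to describe this masked review.

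The cost is wording in the protocol and SAP and one masked listing from data management. Sample size and trial procedures do not change. The limit is that investigators may recall their own subjects' arm, so masking will be partial.

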6.4 Statistical methods

This study will use SAS9.4 or above for statistical analysis. Statistical description shall be performed for all data, including baseline data, all effectiveness indicators, and all safety indicators, etc.

For quantitative variables, descriptive statistics will include number of subjects, mean, standard deviation, median, upper and lower quartiles, minimum, and maximum.

For qualitative variables, descriptive statistics will include the number of subjects and percentages.

Statistical test for the primary efficacy indicators is carried out with two-sided α =0.05. When P is less than 0.05, the inter-group difference is considered statistically significant.

Test hypotheses for the primary efficacy indicators:

Null hypothesis H₀: The overall performance success rate p_1 in the investigational device group is inferior to the p_2 of the control device group ($p_1 \le p_2$ - δ).

Alternative hypothesis H₁: The overall performance success rate p_1 in the investigational device group is non-inferior to the p_2 of the control device group $(p_1 > p_2-\delta)$.

Where $\delta = 5\%$ is the non-inferiority margin, which is the range of differences not considered clinically significant.

For the comparison of the main efficacy indicators between groups, the chi-square test or Fisher's exact test is adopted, and the confidence interval method is used for statistical inference to separately calculate the success rate of each group and the rate difference as well as two-sided 95% confidence interval between the two groups. If the lower limit of two-sided 95% CI > -5%, H₀ is rejected and the overall performance success rate of the investigational device group can be considered non-inferior to the control device group.

Descriptive analysis (quantitative or qualitative description) is performed for the secondary efficacy indicator, the safety evaluation indicators and other evaluation indicators. For categorical variables, summary statistics will include the number of subjects and percentage. For

the description of adverse event, the cases of adverse events will also be summarized. For continuous variables, summary statistics will include the number of subjects, mean, standard deviation, median, upper and lower quartiles, minimum, and maximum. For indicators that require statistical inference, inter-group comparison of quantitative indicators is verified by t-test or Wilcoxon rank sum test based on data distribution characteristics; categorical indicators are verified by χ^2 test or Fisher's exact test; ranked data is verified by Wilcoxon rank sum test.

6.5 Subject number, flush syringe treatment assignment or randomization

6.5.1 Subject number

Each subject will receive a unique screening number, and once a subject has been assigned a screening number, this screening number cannot be assigned to other subjects. This screening number must be recorded on the screening form at each site. Screening numbers will be assigned in the order in which subjects are screened. The screening results shall be recorded in a screening form. Data on the screened subjects, including reasons for screening failure, shall also be input into the electronic case report form (eCRF).

6.5.2 Flush syringe treatment assignment or randomization

The random number of the subject will be provided by the statistical analysis unit commissioned by the sponsor, and the random assignment table of the subject will be generated using SAS9.4 or above. Given the number of seeds and block length, subjects are randomly assigned to the trial and control groups in a 1:1 ratio through a block randomization method.

The random number of the subjects is a 3-digit "site number". If the serial number is less than 3 digits, "0" is added to the front so as to make up 3 digits.

Subject randomization is completed by an Interactive Web Response System (IWRS). Systematic randomization work will be carried out by the investigator or relevant personnel authorized by the investigator. After the successful screening of subjects in each center, the investigators or other authorized personnel log in to the randomization system to obtain the random number and corresponding group information, then study nurses perform the trial intervention according to the random assignment results.

6.6 Handling of missing values and outliers

All missing, unused or incorrect data (including midway withdrawal and exit) and unreasonable data will be discussed and finalized by the investigator, sponsor and biostatistician.

Unless otherwise stipulated, missing values of all analysis indicators will not be filled.

7. Monitoring Plan

According to the requirements in *Good Clinical Practice for Medical Devices*, the sponsor shall undertake monitoring responsibilities for the medical device clinical trial, formulate standard operating procedures for monitoring and select monitors who conform to the requirements to fulfill the responsibilities of monitoring:

The monitor number and monitoring frequency shall be commensurate with the complexity of the trial and the number of clinical trial institutions participating in this trial.

The monitors shall be properly trained, be familiar with GCP and relevant laws and regulations, have relevant professional background expertise, be familiar with relevant research materials of investigational medical devices and clinical information of similar products, clinical trial protocol and related documents, and be able to effectively perform monitoring responsibilities.

The monitors shall abide by the standard operating procedures for monitoring formulated by the sponsor, and urge the clinical trial of medical devices to be implemented in accordance with the clinical trial protocol. The aspects to be monitored include the compliance with clinical trial protocol, GCP and relevant laws and regulations by the clinical trial institutions and the

investigators during the conduct of the clinical trial, the signing of informed consent by subjects, screening, follow-up, rights and security protection, management and use of investigational device and control device, management and use of biological samples, handling of adverse events and device defects, reporting of safety-related information, data records of clinical trial and completion of case report forms etc. The monitors shall report to the sponsor in writing after each monitoring which shall include the name of the monitor, monitoring date, monitoring time, site monitored, aspects monitored, name of investigator, project completion information, issues identified, conclusion and the corrective measures taken for the mistakes and omissions etc.

8. Data Management

Data managers shall prepare a data management plan (DMP) according to project requirements and carry out various specific data management work according to the DMP to ensure the authenticity, integrity and traceability of clinical trial data.

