12.1.3 Correlation of adverse event with devices

Five criteria that investigators will use for judging the relationship between adverse events and study devices. Among them, "definitely related, probably related, and possibly related" will be determined to be adverse events related to the study devices.

(1) Definitely related: It conforms to the known reaction type of the device used, conforms to a reasonable time sequence after treatment, the adverse event cannot be explained by other reasons, the adverse event is alleviated or disappear after the treatment is stopped, the adverse event reappears after reuse, and the adverse event cannot be explained by the subject's current disease;

(2) Probably related: It conforms to the known reaction type of the device used, conforms to a reasonable time sequence after treatment, the adverse event cannot be explained by other reasons, the adverse event is alleviated or disappear after the treatment is stopped, and it is impossible to judge whether the adverse event will occur again after reuse, the adverse event cannot be explained by the subject's current disease;

(3) Possibly related: It conforms to the known reaction type of the device used, conforms to a reasonable time sequence after treatment, the adverse event cannot be explained by other reasons, the adverse event may be alleviated or disappear after treatment is stopped, and it is impossible to judge whether the adverse event will occur again after reuse, the adverse event can be explained by the subject's current disease;

(4) Possibly unrelated: It conforms to the known reaction type of the device used, conforms to a reasonable time sequence after treatment, the adverse event can be explained by other reasons, the adverse event may be alleviated or disappear after treatment is stopped, and it is impossible to judge whether the adverse event will occur again after reuse, the adverse event can be explained by the subject's current disease;

(5) Unrelated: It does not conform to the known reaction type of the device used, does not conform to a reasonable time sequence after treatment, the adverse event can be explained by other reasons, the adverse event does not alleviate or disappear after treatment is stopped, and the adverse event does not occur again after reuse, adverse events can be explained by the subject's current disease.

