6. STATISTICAL ANALYSIS METHODS

6.1 General principles

This study will use SAS 9.4 software or the higher version for statistical analysis.

All statistical tests are conducted using two-sided tests and a P-value less than 0.05 will be considered statistically significant (unless otherwise specified). In this study, hypotheses and statistical inferences are made only for the primary effectiveness indicators, and the intergroup comparisons for the remaining indicators are exploratory analyses.

For the description of quantitative indicators, the number of cases (missing), mean, standard deviation, median, minimum, maximum, and first quartile and third quartile are calculated. The decimal places of the minimum and maximum are kept the same as the original data, but the decimal places of the mean, standard deviation, and median are one more than the original data, but usually, the maximum number of decimal places does not exceed four decimal places.

Qualitative indicators are described by the number of cases and percentages of each category. The percentages are calculated using the non-missing data in each analysis set. Percentages are retained to one decimal place.

All numerically derived variables are retained to two decimal places, unless otherwise specified.

The treatment of missing data will be described in Section 7, otherwise all missing data will be left unfilled.

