6.4 Safety evaluation

(1) Evaluation Indicators

Adverse events and serious adverse events

(2) Evaluation method

Safety analysis is conducted based on safety set (SS).

The Medical Dictionary For Regulatory Activities (MedDRA) version 25.1 is used for adverse event coding. Adverse events that occur prior to the start of the flush syringe treatment are only shown in the list.

Adverse events that occur not earlier than the use of investigational device or that exist before the use of investigational device but get severe at or after the use of the investigational device are considered TEAEs. If multiple adverse events of the same preferred term (PT) occur in the same subject, the most serious one is used for the final intergroup comparison.

The number, frequency and proportion of TEAEs and investigational device-related TEAEs occurring in each group are tabulated and summarized according to system organ classification (SOC), preferred term (PT) and severity. If the same adverse event occurs multiple times in the same subject, the most serious one is used for analysis.

Severe TEAEs, TEAEs leading to study discontinuation, and TEAEs leading to death are summarized for each group by system organ classification (SOC) and preferred term (PT), respectively.

Adverse events related to the investigational device include those judged as "definitely related, likely related, and probably related" in relation to the investigational device.

Adverse events leading to study discontinuation (including whether the adverse event leads to withdrawal from the trial) are judged as "yes".

Adverse events leading to death (including prognosis) are selected as "Death".

All adverse events during the study are detailed in the list.

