7. DATA PROCESSING AND CONVERSION

7.1 Processing of missing data regarding primary effectiveness

The primary effectiveness indicators are not filled.

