7.2 Missing of severity of adverse events

The severity of adverse events prior to flush syringe treatment is missing and is filled using "moderate". Missing of severity of adverse events occurring after the start of flush syringe treatment is filled using "severe" and these filled-in values are used for summary of occurrence rate only and are presented as original values in the final list.

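### SAP 7.2 fills a blank adverse event severity with the worst grade but has no rule for a blank device relationship, so such an event would drop out of the device-related table

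*Protocol*

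**What the plan says.** Protocol 6.6 has two sentences on missing data. The first sends missing and unreasonable data to a joint decision; they "will be discussed and finalized by the investigator, sponsor and biostatistician". The second sets the default: "Unless otherwise stipulated, missing values of all analysis indicators will not be filled".

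SAP 6.1 carries the default over and says where exceptions are to be found: "The treatment of missing data will be described in Section 7, otherwise all missing data will be left unfilled".

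SAP Section 7 has two items. On the primary endpoint, 7.1 says: "The primary effectiveness indicators are not filled". On adverse events, 7.2 fills a missing severity only. An event before the flush is set to moderate. For later events the rule reads "Missing of severity of adverse events occurring after the start of flush syringe treatment is filled using" the grade severe. The filled grade is used only in the rate summaries, and the listing keeps what was recorded.

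SAP 6.4 tabulates all TEAEs and, separately, device-related TEAEs. The second group is defined by the investigator's judgement: "Adverse events related to the investigational device include those judged as" definitely, likely or probably related. Protocol 12.1.3 names the related grades differently: definitely, probably and possibly related.

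**The concern.** Severity and device relationship are two fields of the same adverse event record, and Protocol 12.1.4 asks the investigator to determine both. The SAP accepts that severity may still be missing at analysis and then assumes the worst. It has no matching provision for relationship. An event with a blank relationship is in none of the related grades, so by default it is tabulated as if it had been judged unrelated. One gap is thus handled conservatively, and the other in the direction that favours the device.

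Safety is part of the trial objective, and the device-related table is the summary that attributes harm to the syringe. The exposure is one flush with one hour of follow-up. If few events occur, which is an assumption because the documents give no rate, a single blank field could decide whether an arm shows any device-related event at all.

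**Working it through.** **Inputs**

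- Default of no filling: Protocol 6.6 and SAP 6.1.
- Exceptions: SAP 7.1 (none for the primary endpoint) and SAP 7.2 (severity only).
- Definition of a device-related event: SAP 6.4.
- Arm size: 378 subjects allocated 1:1, so 378/2 = 189, as SAP 3.3 states for the test group. The nurse plan gives the same number: 63 nurses × 3 devices per arm = 189.
- Adverse event rate and share of blank relationship fields: not given in either document.

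**Step 1. The two blanks side by side, for a TEAE**

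| | Severity blank | Relationship blank |
|---|---|---|
| Rule in SAP Section 7 | Set to severe | None |
| Rule that then applies | SAP 7.2 | SAP 6.1: "otherwise all missing data will be left unfilled" |
| All-TEAE table | Counted, as severe | Counted |
| Device-related TEAE table | Counted if judged related | Not counted |
| Listing | Shown blank | Shown blank |

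The fourth row of the table combines two provisions. SAP 6.1 forbids putting a value in the field, and SAP 6.4 admits an event to the device-related group on the strength of a judgement that, for this event, does not exist.

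**Step 2. Size per affected subject**

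The plan has no figure of its own on this point, so there is none to reproduce. For an arm of N subjects of whom k truly had a device-related TEAE, with b of them showing only a blank relationship:

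reported rate = (k − b)/N; true rate = k/N; shortfall = b/N.

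With N = 189 and b = 1, the shortfall is 1/189 = 0.53 percentage points. For assumed values of k:

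| k (assumed) | True rate | Reported rate, b = 1 |
|---|---|---|
| 1 | 1/189 = 0.53% | 0/189 = 0% |
| 2 | 2/189 = 1.06% | 1/189 = 0.53% |
| 4 | 4/189 = 2.12% | 3/189 = 1.59% |
| 10 | 10/189 = 5.29% | 9/189 = 4.76% |

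With b = 0 the shortfall is zero. A subject who also has another TEAE judged related is already in the numerator, so a blank on a second event does not change the subject-level rate.

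**Step 3. Expected size if blanks are rare**

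If a share m of truly related events is blank at lock, the expected loss is k × m. Taking m from 0 to 10% as an assumption, the loss is 0 to 0.2 events for k = 2, 0 to 0.4 for k = 4, and 0 to 1.0 for k = 10.

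**The case against.** The strongest reply is that a blank relationship should not reach the analysis. The investigator must judge it (Protocol 12.1.4). Data are checked by program and by hand, and doubtful points are queried (8.5). The monitor confirms completeness (8.4). Missing data go to joint review (6.6). The database is locked only when confirmed complete and accurate (8.9). Even if a blank survived, the event would still appear in the all-TEAE table and in the listing. No decision hangs on the device-related table, since SAP 6.1 limits formal inference to the primary endpoint.

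Much of this stands. It makes the problem unlikely, visible and small. It does not remove the inconsistency, because the same safeguards cover severity and the SAP still wrote a worst-case rule for it. Joint review does not close the gap either. Protocol 6.6 says who decides but not what the outcome should be. In an open trial with no blind review (Protocol 8.8), those parties would settle a blank relationship without any safeguard of blinding.

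Two further replies have some force. SAP 6.4 does not say in terms that a blank counts as unrelated, and table layouts are in a separate document (SAP Section 9) that might provide a row for missing values. Exclusion from the device-related count is what the written rules produce, but no sentence states it. Also, counting blanks as related is a convention; a separate row for missing relationship would be just as transparent.

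A reader might go further and infer that device-related harm is under-counted in this trial, or that the comparison is tilted towards the test device. The documents support neither. Under-counting needs a blank that survives to lock on an event that was truly related, and nothing shows that this will happen. If the event was unrelated, leaving it out is correct. Blanks can fall in either arm.

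**Conclusion.** The point holds in conditional form. Under SAP 6.1, 6.4 and 7.2 taken together, a TEAE whose device relationship is still blank at lock would be missing from the device-related table. A blank severity on the same event would be set to the worst grade. If the event was truly related, the device-related rate in that arm would be too low by 0.53 percentage points per affected subject. That assumes 189 subjects in the arm and no other related event in that subject. With no blanks the effect is nil. How often a blank would occur cannot be estimated from the documents.

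The primary analysis and the non-inferiority conclusion are untouched. This is a low-cost improvement to the safety section and should be made before lock; it is not a flaw that threatens the trial.

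**What to change.** Add one sentence to SAP 7.2, named as an exception to SAP 6.1 and Protocol 6.6: a TEAE whose relationship to the study device is missing is counted as device-related in the summary tables, in both arms; the number of such events is shown with the table; and the listing keeps the blank. This follows the approach that SAP 7.2 already takes for severity.

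In the same edit, reconcile the related grades. SAP 6.4 lists definitely, likely and probably; Protocol 12.1.3 lists definitely, probably and possibly. This may only be translation, but read literally the SAP's list does not name the protocol's possibly related grade.

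The cost is one sentence, one line of code and a wording correction. The downside is a slight overstatement of the device-related rate, by the same 0.53 points per subject, if a blank event was in truth unrelated. Showing the number of blank events lets the reader see how much of the count rests on the rule.
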